1. PROJECT TITLE

Cryoanalgesia to Prevent Acute and Chronic Pain following Surgery: A Randomized, Double-Masked, Sham-Controlled Study

3. FACILITIES

UCSD hospitals and the UCSD CTRI

4. ESTIMATED DURATION OF THE STUDY

Five years (including follow-up and analysis)

5. LAY LANGUAGE SUMMARY OR SYNOPSIS (no more than one paragraph)

Knee and shoulder arthroplasty, rotator cuff repair, video-assisted thoracoscopic surgery, and skin grafting for burn repair all result in both acute, and frequently persistent post-surgical pain. In addition, following mastectomy or limb amputation, pain perceived in the part of the body that no longer exists often develops, called "phantom" breast or limb pain, respectively. The exact reason that chronic and phantom pain occur is unclear, but when a nerve is cut changes occur in the brain and spinal cord that are associated with persistent pain. The negative feedback-loop between the injured body part and the brain can be stopped by putting local anesthetic—called a "nerve block"—on the injured nerve, effectively keeping any "bad signals" from reaching the brain. However, a single-injection block lasts less than 24 hours; and, even a continuous peripheral nerve block is generally limited to less than one week. The negative pain signals from the surgical insult continue for multiple weeks or months. In contrast to local anesthetic-induced nerve blocks, a prolonged block lasting a few weeks/months may be provided by freezing the nerve using a process called "cryoneurolysis". *The ultimate objective of the proposed line of research is to determine if cryoanalgesia is an effective adjunctive treatment for pain in the period immediately following mastectomy or limb amputation; and, if this analgesic modality decreases the risk of persistent postoperative pain, or "chronic" pain. The objective of the proposed pilot study is to optimize the protocol and collect data to power subsequent, definitive clinical trials.*

6. SPECIFIC AIMS

The ultimate objective of the proposed line of research is to determine if cryoanalgesia is an effective adjunctive treatment for pain in the period immediately following various painful surgical procedures; and, if this analgesic modality decreases the risk of persistent postoperative pain, or "chronic" pain. *The objective of the proposed pilot study is to optimize the protocol and collect data to power subsequent, definitive clinical trials.*

Specific Aim 1: To determine if, compared with current and customary analgesia, the addition of cryoanalgesia decreases the incidence and severity of post-surgical pain.

Hypothesis 1a (primary): The severity of surgically-related pain will be significantly decreased on postoperative day 2 with the addition of cryoanalgesia as compared with patients receiving solely standard-of-care treatment.

Hypothesis 1b: The incidence of chronic pain will be significantly decreased one year following surgery with the addition of cryoanalgesia as compared with patients receiving solely standard-of-care treatment.

Hypothesis 1c: The severity of chronic pain will be significantly decreased one year following surgery with the addition of cryoanalgesia as compared with patients receiving solely standard-of-care treatment.

[figure not shown]
Specific Aim 2: To determine if, compared with current and customary analgesia, the addition of cryoanalgesia improves postoperative functioning.

Hypothesis 2a: Following primary unilateral knee and shoulder arthroplasty as well as rotator cuff repair, joint range of motion will be significantly increased within the year following surgery with the addition of cryoanalgesia as compared with patients receiving solely standard-of-care treatment.

Hypothesis 2b: Following video-assisted thoracoscopic surgery, inspiratory spirometry will be improved within the month following surgery with the addition of cryoanalgesia as compared with patients receiving solely standard-of-care treatment.

7. BACKGROUND AND SIGNIFICANCE

Hypothesis 1a (acute pain): Pain within the first week after a mastectomy or limb amputation is often intense, with breakthrough pain as measured with a Numeric Rating Score (NRS; 0-10, 0 = no pain, 10 = extreme pain) a median of 7; and 25% of women describing a “continuous aching pain” the day following mastectomy.¹ Similarly, pain following knee and shoulder arthroplasty, rotator cuff repair, video-assisted thoracoscopic surgery, and burn-related skin grafting also can result in significant postoperative pain. Intense analgesia may be provided with a peripheral nerve block, which involves the placement of long-acting local anesthetic adjacent to the peripheral nerves that innervate the surgical site.² Unfortunately, the longest-acting local anesthetics clinically available have a duration of less than 24 hours, after which patients are mainly dependent upon opioids, which result in inadequate analgesia and undesirable side effects such as pruritis, nausea, vomiting, constipation, urinary retention, sedation, and respiratory depression. Local anesthetic-based analgesia may be extended using a continuous perineural infusion via a percutaneous catheter; but, this technique is usually limited to a few days due to infection risk, catheter dislodgement, and anesthetic consumption.³ The pain of these surgical procedures can last weeks, and is often exacerbated by physical therapy, itself critical to optimizing outcomes following knee and shoulder surgery.

An alternative analgesic technique is **cryoneurolysis**, consisting of the application of exceptionally low temperatures to *reversibly* ablate peripheral nerves, resulting in temporary pain relief termed “*cryoanalgesia*”.⁴ The intense cold temperature at the probe tip produces Wallerian degeneration—a reversible breakdown of the nerve axon—subsequently inhibiting transmission of afferent and efferent signals. Because the nerve endoneurium, perineurium, and epineurium remain intact, the axon regenerates along the exoskeleton at a rate of approximately 1-2 mm/day. While cryoneurolysis of peripheral nerves through surgical incisions has been commonly used to treat pain since 1961, the development of cryo probes that may be inserted percutaneously promise a revolution in the use of this modality. The combination of newly-designed narrow-gauge probes (immediate right) and ultrasound now make percutaneous cryoanalgesia as simple as placing a peripheral nerve block: the probe tip is inserted adjacent to the target nerve under ultrasound guidance, and a series of 1-minute freezing cycles are administered followed by probe withdrawal.⁵ *The procedure is essentially the same as placing an ultrasound-guided peripheral nerve block; however, instead of injecting local anesthetic, a gas circulates through the probe, inducing cold at the tip and freezing the target nerve.* Nothing remains within the patient and there is no external equipment to prepare or manage. Importantly, cryoneurolysis and the cryo probes are already approved by the United States Food and Drug Administration for the treatment of acute and chronic pain, so no additional regulatory approval is required for the proposed clinical trial.

Theoretical benefits of cryoneurolysis include an ultra-long duration of action without opioid involvement, no catheter management/removal, the lack of an infusion pump and anesthetic reservoir to carry, an extraordinarily-low risk of infection (approaching zero), and no risk of local anesthetic toxicity, catheter dislodgement or leakage. With a single 8-minute percutaneous cryoneurolysis procedure consisting of several freeze/defrost cycles, a truncation of sensory nerve conduction is induced for 6-8 weeks (motor neurons variable) with the complete restoration of nerve structure and function following remyelination. Cryoneurolysis offers the possibility of potent, side effect-free analgesia outlasting the surgical pain, and obviating the need for postoperative opioids.

Hypothesis 1b and 1c (persistent, post-surgical chronic pain): Following mastectomy and other painful surgical procedures, moderate to severe pain within the acute postoperative period is closely associated with subsequent persistent postsurgical pain lasting months⁶ or even years.^{7,8} Such chronic pain has an incidence of 30-73%,⁸⁻¹⁰ and is strongly correlated with depression and anxiety.¹¹ There is evidence that intense analgesia immediately following surgery may decrease the incidence and/or severity of chronic pain.^{12,13} Potent analgesia can be provided with intercostal nerve blocks in which local anesthetic is percutaneously injected adjacent to the peripheral nerves innervating the

breast.^{1,13} While single-injection nerve blocks have a duration of approximately 8 hours,¹⁴ they have been associated with a lower incidence of chronic pain 4-12 months after mastectomy.^{13,15,16} Extending the block to 60 hours can further decrease the incidence and severity of chronic pain.¹⁷

Furthermore, while the prevalence of post-mastectomy phantom breast pain—painful sensations perceived in the breast that is no longer present¹⁸—varies greatly, it has been reported as high as 44%.⁹ There is prospective clinical evidence that following upper and lower extremity amputation, continuous brachial plexus, sciatic, and femoral nerve blocks may decrease the incidence and/or severity of phantom limb pain.^{19,20} Using cryoneurolysis, a dense, multi-week peripheral nerve block may be provided, offering not only the possibility of the block outlasting the surgical pain, but enabling an opioid-free recovery and dramatically decreasing the risk of chronic pain.

Thirty-five to 98 percent of limb amputees (depending on the study) develop chronic, intractable pain perceived as being from the missing limb, a phenomenon termed “phantom pain”.²⁰ The pain is usually described as “shooting, stabbing, boring, squeezing, throbbing, and burning”.²¹ Unfortunately, phantom pain resolves in only 16% of afflicted individuals (with or without treatment). The rest will experience phantom pain for the remainder of their lives, with most becoming dependent upon chronic opioid use to gain even a small degree of relief. There is currently no reliable, definitive treatment for phantom pain.

A “continuous peripheral nerve block”—administration of local anesthetic through a percutaneously-inserted perineural catheter—may provide a prolonged block.³ In an uncontrolled series of 19 patients with phantom pain treated with continuous blocks, pain intensity was halved at 1 and 6 months.²⁰ However, the sensory block using this technique is frequently incomplete and/or inconsistent; the infusion duration usually limited to less than one week due to the risk of infection and difficulty of carrying a large bag of local anesthetic; and catheter dislodgement is relatively common.³ A more reliable, complete block of longer duration would theoretically increase any treatment effects for phantom pain, while reducing these inconveniences and complications. Cryoneurolysis offers such a dense, multi-week peripheral nerve block.

Given chronic pain’s enormous costs to individuals and society—and the intractable, currently-untreatable nature of chronic pain with concurrent opioid dependence—it is imperative that an effective prevention strategy be developed. If our study demonstrates that ultrasound-guided percutaneous cryoneurolysis prevents chronic pain, the resulting impact on patients will be **immediate and profound**, as (1) healthcare providers within the United States already have expertise placing ultrasound-guided peripheral nerve blocks; (2) cryoneurolysis is a relatively inexpensive, single-procedure treatment with few complications; and (3) cryoanalgesia is already approved by the United States Food and Drug Administration.

9. RESEARCH DESIGN AND METHODS

All subjects would continue to receive standard and customary postoperative analgesics, so there is no risk of subjects receiving a lower degree of analgesia than if they otherwise did not enroll in the study. The cryoneurolysis procedure will be done in addition to our current UCSD standard practice.

Study Overview

Day 0 Subjects randomized and cryoneurolysis/sham procedure administered

Days 0-4, 7, 14, 21 Pain levels, opioid consumption, and other end points collected [inspiratory spirometry for hospitalized subjects following video-assisted thoracoscopic surgery will occur at various time points as part of standard care and will be collected via EPIC]

Months 1, 3, 6, 12 Brief pain inventory administered [range-of-motion measurements following knee and shoulder arthroscopy as well as rotator cuff repair will occur at various time points as part of standard care and will be collected via EPIC]

Year 3 Cancer recurrence investigated for subjects with cancer-related procedures

Subjects will be individuals undergoing unilateral or bilateral mastectomy; upper or lower limb amputation; primary, unilateral total knee or shoulder arthroplasty; primary, unilateral rotator cuff repair; video-assisted thoracoscopic surgery; and burn-related skin grafting of the lateral thigh. Those who consent to participate in this study will have standard preoperative peripheral nerve blocks administered and catheters inserted: paravertebral blocks or a fascial plane block (e.g., erector spinae plane block) for mastectomy, femoral/sciatic for lower limb amputation, brachial plexus (or terminal nerves) for upper limb amputation; femoral or adductor canal for total knee arthroplasty; interscalene for shoulder arthroplasty or rotator cuff repair; thoracic epidural for video-assisted thoracoscopic surgery (VATS); and lateral femoral cutaneous nerve for skin grafting of the lateral thigh.

Treatment group assignment (randomization). Subjects with successfully-administered peripheral nerve blocks (defined by sensory changes in the appropriate nerve distribution) will be allocated to one of two possible treatments:

1. *cryoneurolysis*
2. *sham cryoneurolysis (placebo control)*

Randomization will be stratified by surgery type (e.g., mastectomy, upper limb amputation, and lower limb amputation). Computer-generated randomization lists will be used to create sealed, opaque randomization envelopes with the treatment group assignment enclosed in each envelope labeled with the randomization number.

The specific nerves targeted will depend on the surgical site: intercostal nerves (4 levels depending on the specific surgical approach) for mastectomy; femoral/sciatic for lower limb amputation, brachial plexus (or terminal nerves) for upper limb amputation; infrapatellar branch of the saphenous nerve for knee arthroplasty; suprascapular nerve for shoulder surgery; intercostal nerves for VATS procedures, and the lateral femoral cutaneous nerve for skin grafting of the lateral thigh. The cryoneurolysis sites will be cleansed with chlorhexidine gluconate and isopropyl alcohol. Using the optimal ultrasound transducer for the specific anatomic location and subject anatomy (linear vs curvilinear array), the target nerves will be identified in a transverse cross-sectional (short axis) view.

Cryoneurolysis probes are available for a console neurolysis device (PainBlocker, Epimed, Farmers Branch, Texas) that either (1) pass nitrous oxide to the tip inducing freezing temperatures; or, (2) vent the nitrous oxide at the base of the probe so that no gas reaches the probe tip, resulting in no temperature change. Importantly, these probes are indistinguishable in appearance, and therefore treating physicians, subjects, and all clinical staff will be masked to treatment group assignment [only the physician/investigator performing the cryoneurolysis will be unmasked]. An angiocatheter/introducer may be inserted beneath the ultrasound transducer and directed until the probe tip is immediately adjacent to the target nerve (lidocaine 2% will be administered, as needed, to anesthetize the angiocatheter track). The angiocatheter needle will be removed, leaving the angiocatheter through which the appropriate Epimed probe will be inserted until it is adjacent to the target nerve. The cryoneurolysis device will be triggered using 3 cycles of 2-minute gas activation (active or sham) separated by 1-minute defrost periods. For active probes, the nitrous oxide will be deployed to the tip where a drop in temperature to -70°C will result in cryoneurolysis. For the sham probes, the nitrous oxide will be vented prior to reaching the probe shaft, resulting in a lack of perineural temperature change. The process will be repeated with the same treatment probe for any additional nerves (e.g., all nerves will receive either active cryoneurolysis or sham/placebo, and not a mix of the two possible treatments).

FDA Approval. Cryoneurolysis has been FDA approved since May 28, 1976, with continuous clinical use since then. The specific device used for this study, the Epimed Painblocker, has been FDA cleared for use to treat both acute and chronic pain since April 30, 1986, as a significant risk device. The Painblocker is NOT considered experimental or investigational (there is no IDE); and, we are using the device in a manner that the FDA approved of regarding the subject population and purpose (treating acute pain).

Outcome measurements (end points). Staff blinded to treatment group assignment will perform all measures and assessments, which will include:

Pain: measured on the 11-point NRS of pain intensity

Brief Pain Inventory: The Brief Pain Inventory (short form) is an instrument specifically designed to assess pain and its impact on physical and emotional functioning within the previous 24 hours.^{22,23} It has established reliability and validity, with minimal inter-rater discordance, and is recommended by

the Initiative on Methods, Measurement, and Pain Assessment in Clinical Trials (IMMPACT) consensus statement.²⁴ The Brief Pain Inventory is comprised of three domains: (1) *pain*, with four questions involving “worst”, “average”, “least”, and “current” pain levels using a 0-10 Numeric Rating Scale (NRS; 0 = no pain; 10 = worst pain imaginable); (2) percentage of *relief* provided by pain treatments with one question (reported score is the percentage divided by 10 and then subtracted from 10: 0 = complete relief, 10 = no relief); and, (3) *interference* with 7 questions involving physical and emotional functioning using a 0-10 Likert scale (0 = no interference; 10 = complete interference). The use of both single items (e.g., average pain) and the composite score (0 = optimal; 120 = worst possible) is supported by the IMMPACT recommendations for assessing pain in clinical trials.²⁵⁻²⁷

Opioid consumption

Sleep disturbances: due to surgical pain

Range of motion: measured with a standard goniometer

Forced expiratory volume in 1 second (FEV1): measured with a standard inspiratory spirometer

Cancer recurrence: for subjects who underwent the surgical procedure related to a primary cancer, subjects' records will be investigated for indications of cancer recurrence up to 3 years following catheter placement (including estrogen receptor status as + or -). Patients may be contacted by phone if records suggest that the patient has not returned to the original surgeon within the previous 12 months.

The questionnaire will differentiate among multiple dimensions of breast and limb pain:

Phantom pain: painful sensations referred to the lost body part (breast or limb).

Phantom breast/limb sensations: non-painful sensations referred to the lost body part.

Wound pain: painful sensations localized to the portion of the body still present.

Summary of post-enrollment assessments (color added for clarity)

Time Point:	Postoperative Days								Postoperative Months			
	0	1	2	3	4	7	14	21	1	3	6	12
Opioid consumption	•	•	•	•	•	•	•	•	•	•	•	•
Average & worst pain [NRS]	•	•	•	•	•	•	•	•				
Brief Pain Inventory									•	•	•	•
Average & worst phantom pain									•	•	•	•
Incidence; duration each episode									•	•	•	•
Average & worst wound pain									•	•	•	•
Incidence; duration each episode									•	•	•	•

Difficulty sleeping due to pain?	•	•	•	•	•	•	•				
Awakenings due to pain	•	•	•	•	•	•	•				
Nausea (0=none, 10=vomited)	•	•	•	•	•	•	•				

* In addition to the above, for knee and shoulder surgery joint range of motion will be measured at various time points between 1-12 months as part of standard postoperative care; and for VATS, FEV1 will be measured at various time points during hospitalization as part of standard postoperative care.

Statistical Analysis. The limb amputation, total knee and shoulder arthroplasty, rotator cuff repair, VATS, and skin grafting subjects will be included in pilot studies to help power future clinical trials, so we will enroll a convenience sample and not have a pre-determined primary endpoint or statistical plan. However, the end points of most interest will be average pain score on postoperative day 2 for shoulder arthroplasty and skin grafting subjects, range-of-motion at 6 weeks for the rotator cuff repairs, range-of-motion for knee arthroplasty, and FEV1 for the VATS procedures.

For the subjects having mastectomy, we will power this study for an acute pain end point which will provide conclusive results for that end point; but, the data will also be used to help power a subsequent large, multicenter clinical trial for a chronic pain-related end point (which will require far more subjects than we will enroll for the current study).

For the mastectomy subjects, sample size calculations are centered around the hypothesis that cryoneurolysis decreases the incidence and severity of post-mastectomy pain in the week following surgery. To this end, the primary outcome is the average NRS (as administered as part of the Brief Pain Inventory) queried on the afternoon of postoperative day 2. The difference in the distribution of NRS between groups will be assessed using the Mann-Whitney U test. We approximate power using the two-sample t-test. Assuming a standard deviation of 2.25 NRS points,² and minimum clinically meaningful difference of 2 NRS points, n=30 patients per group provide 86% power with two-sided $\alpha=5\%$.

The t-test approximation was confirmed by simulating integer valued NRS scores in the range 0 to 10. One group was simulated by rounding normally distributed data with mean 1.5 and standard deviation 2.5 (resulting in median of 2 and interquartile range 0 to 3); and the other with mean 3.5 and standard deviation 2.5 (resulting in median of 4 and interquartile range 1 to 5). Note these resulting summary statistics are consistent with Ilfeld et al (2014). When 10,000 trials were simulated under these assumptions, the Mann-Whitney U test provided 89.5% power, and Type I error was maintained at 4.85%.

Differences between groups in demographic variables and secondary endpoints will be assessed with the Mann-Whitney U test for continuous or ordinal data, and Fisher's Exact test for categorical data. Box-and-whisker plots will be used to visualize distributions by group.

R version 3.4.4 ([R-project.org](https://www.R-project.org)) was used for sample size calculations and simulations; and the most recent version of R will be used at the time of analysis.

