10. HUMAN SUBJECTS

A convenience sample of subjects undergoing limb amputation (n=60), mastectomy (n=60), knee arthroplasty (n=60), shoulder arthroplasty and rotator cuff repair (n=60), VATS (n=60), and skin grafting of the lateral thigh (n=60) will be enrolled, with an additional 20 permitted to replace drop-outs. This will total up to 380 subjects.

Inclusion criteria: Adult patients of at least 18 years of age, (1) scheduled for a primary, unilateral total knee or shoulder arthroplasty, primary unilateral rotator cuff repair, VATS procedure, skin grafting of the lateral thigh, unilateral or bilateral mastectomy, or limb amputation distal to the femoral/humeral head and including at least one metatarsal/metacarpal bone; (2) a single-injection or continuous peripheral nerve block or epidural infusion planned for perioperative analgesia; and, (3) accepting of a cryoneurolysis procedure.

Exclusion criteria: (1) chronic opioid use (daily use within the 2 weeks prior to surgery and duration of use > 4 weeks); (2) pregnancy; (3) incarceration; (4) inability to communicate with the investigators; (5) morbid obesity (body mass index > 40 kg/m²); and, (6) possessing any contraindication specific to cryoneurolysis such as a localized infection at the treatment site, cryoglobulinemia, cold urticaria and Reynaud's Syndrome.

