12. INFORMED CONSENT

When a prospective subject desires, they will be provided information on the study purpose and protocol, as well as have any questions answered. Candidates who meet inclusion and exclusion criteria and desire study enrollment will be scheduled for their initial treatment. Written informed consent will be attained prior to any measurements or procedures the morning of surgery. This will occur in private patient care rooms, so that subjects may feel comfortable asking questions.

We do not foresee any issues relevant to the mental capacity of the potential human subjects. Written, informed consent will be attained prior to any study procedures or measurements. Following a history and physical by the site director, subjects will have an intravenous line inserted, external monitors placed, oxygen delivered by face mask, and conscious sedation provided for perineural catheter insertion. Therefore, subjects will not be sedated until following the written, informed consent process is completed.

Subjects will be provided privacy and time for decision making both in the study description/explanation telephone call to an investigator or research coordinator, as described above; and also the morning of the initial treatment using a private patient care room to again review the study, informed consent form, and answer any remaining subject questions. As noted previously, subjects may speak with an investigator by telephone from initial contact through the morning of treatment.

Surrogate consent will not be accepted; therefore, if human subjects cannot provide consent on their own, they will not be offered study enrollment. Consent by an individual's Legally Authorized Representative is unacceptable for study enrollment. Of note, minors (age < 18 years) will not be offered enrollment. Therefore, assent will not be accepted during the informed consent process.

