13. ALTERNATIVES TO STUDY PARTICIPATION

Potential study subjects may simply decline enrollment. They will still receive our standard-of-care analgesics including a continuous peripheral nerve block.

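### Does the primary mastectomy test need stratifying by block modality, given that section 9 describes catheters for all and section 10 also admits a single-injection block?

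*Combined protocol and SAP*

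**What the plan says.** Section 9 (Study Overview) says "Those who consent to participate in this study will have standard preoperative peripheral nerve blocks administered and catheters inserted", then lists the blocks by surgery: "paravertebral blocks or a fascial plane block (e.g., erector spinae plane block) for mastectomy", and further on "thoracic epidural for video-assisted thoracoscopic surgery (VATS".

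Other places also assume a catheter or a continuous block:
- Section 12 describes "conscious sedation provided for perineural catheter insertion".
- Section 13 says of patients who decline: "They will still receive our standard-of-care analgesics including a continuous peripheral nerve block".
- The cancer-recurrence outcome in section 9 runs "up to 3 years following catheter placement".
- Section 15 calls its monitoring the standard for placing a catheter.

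The inclusion criteria in section 10 are wider. They ask for "a single-injection or continuous peripheral nerve block or epidural infusion planned for perioperative analgesia", in one sentence that covers every surgery type.

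Allocation follows a successful block (section 9, Treatment group assignment). Randomisation is stratified by surgery type. The primary mastectomy comparison is an unstratified Mann-Whitney U test of the average NRS on the afternoon of postoperative day 2, with 30 subjects per group.

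**The concern.** Mastectomy is the only cohort powered for a conclusive answer, so a loose end there deserves a check. The lay summary in section 5 says "a single-injection block lasts less than 24 hours; and, even a continuous peripheral nerve block is generally limited to less than one week". On those durations a single injection has worn off by the afternoon of day 2, while an infusion may still be running. If both kinds of subject are enrolled, modality plausibly shifts the primary score.

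Modality is fixed before allocation, so it could properly be used as a stratum or covariate. Leaving it out can cost power and leaves a chance imbalance between arms unadjusted. If a running infusion also masks the benefit of cryoneurolysis, the average effect shrinks.

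**Working it through.** **1. Is there a mixed mastectomy population?** The catheter wording in section 9 governs the list that contains the mastectomy blocks, and sections 12, 13 and 15 and the recurrence outcome agree with it. The section 10 criterion is generic: its epidural option matches only VATS in the section 9 list, so parts of the sentence plainly do not apply to every cohort. The single-injection option may or may not apply to mastectomy. A mix is possible but not shown, and its share is not given.

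**2. The plan's own power figure.** Inputs from section 9: difference 2, SD 2.25, 30 per group, two-sided 5%. Noncentrality = 2 / (SD × √(2/30)).
- SD 2.25: 2 / 0.581 = 3.44; two-sample t power 92.3%.
- SD 2.5: 2 / 0.645 = 3.10; power 86.1%, which matches the stated 86%.

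Simulating as section 9 describes (means 1.5 and 3.5, rounded, limited to 0-10) gives about 83% with the stated SD of 2.5 and about 90% with 2.25; the plan reports 89.5%. The two SDs look interchanged. That is a separate matter, so both are used below.

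**3. Effect of stratifying the test.** Assumptions, none from the documents: single-injection sham mean 3.5; catheter sham mean lower by a gap of 0, 1 or 2 points; treatment lowers the underlying score by 2; the SD applies within modality. Planned Mann-Whitney power, then van Elteren (Wilcoxon stratified by modality), in %, from 100,000 trials per cell:

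| SD | Catheters | Gap 0 | Gap 1 | Gap 2 |
|---|---|---|---|---|
| 2.25 | 50% | 90.1 → 89.1 | 87.9 → 88.5 | 81.8 → 86.9 |
| 2.25 | 80% | 90.1 → 89.2 | 87.9 → 87.8 | 82.2 → 85.2 |
| 2.25 | 90% | 89.8 → 89.0 | 88.1 → 87.7 | 83.2 → 84.6 |
| 2.5 | 50% | 83.0 → 81.9 | 80.6 → 80.9 | 74.6 → 79.1 |
| 2.5 | 80% | 83.1 → 82.1 | 80.4 → 80.2 | 74.5 → 77.2 |
| 2.5 | 90% | 82.9 → 81.9 | 80.8 → 80.2 | 75.6 → 76.5 |

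Overall type I error is 4.8 to 5.1% for both tests.

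**4. Is the fall from 90.1% to 81.8% a shortfall from plan?** Only under the assumption that 2.25 is a within-modality SD. Total variance = within variance + p(1 − p) × gap². At p = 0.5 and gap 2 the added term is 0.25 × 4 = 1, so the total SD becomes √(5.0625 + 1) = 2.46. The setup also lowers the average sham mean from 3.5 to 2.5, which brings in a floor effect at 0: an all-catheter cohort with sham mean 1.5 has 85.1% power.

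Section 9 does not say that its SD is within modality. If mean 3.5 and SD 2.25 describe everyone enrolled, the within-modality SD is √(5.0625 − 1) = 2.02. The planned test then keeps about 90% power at a 2-point gap with 50, 80 or 90% catheters (about 83% with SD 2.5). Stratifying adds roughly 5 points at 50% catheters and 1 at 90%; a shorter run of 4,000 trials with SD 2.5 and a 50% mix gave +5.6.

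**5. Chance imbalance.** With 30, 48 or 54 catheter subjects among 60, the hypergeometric probability that the arms differ by 6 or more is 0.196, 0.104 and 0.024. Within those trials the pooled test rejects a true null in 8 to 9.5% at a 2-point gap and 5.5 to 6.5% at a 1-point gap. The overall rates in step 3 already include these trials.

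**6. Loss of effect under a running infusion.** If the effect vanishes in catheter subjects, planned power is 28 to 35% at 50% catheters, 8 to 9% at 80% and 6% at 90%. The stratified test changes this by -0.4 to -2.3 points, so it is no remedy for that case.

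**The case for a change.** The best case for a change is that pre-specification is cheap. One baseline item and a stratified rank test need no extra subjects. An adjustment chosen after an imbalance is seen would look driven by the data. The protocol's own block durations make modality a natural predictor of the day-2 score, and results by modality would help plan the later trial that section 9 mentions.

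Part of this stands. If both modalities are enrolled, recording modality and showing a stratified result as a sensitivity analysis is sensible, and analysts may do so under the present plan. Whether modality is already recorded cannot be judged, because the case report forms are not in the documents.

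It does not carry through to a change of primary test. The gain needs both a real mix and a gap well above 1 point; otherwise the stratified test gives nothing or loses up to about 1 point. With 90% catheters the smaller stratum has six subjects, and on an unsplit list they all fall in one arm with probability 0.024 and then contribute nothing. Modality is also not special: unilateral or bilateral surgery, and paravertebral or fascial plane block, are equally outside the strata and the test. An unadjusted rank test in 60 subjects is a defensible choice.

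**Conclusion.** The mismatch between sections 9 and 10 is real, and the sentences must be reconciled on which block modality mastectomy subjects have. This is a clerical matter: it alters no endpoint, test or sample size. A mixed mastectomy population is not established. If there were one, the planned Mann-Whitney test would remain valid and unbiased, with type I error near 5%.

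The choice between the planned and a stratified test is a fair trade-off: about -1 point of power with no gap, about 0 at 1 point, and about +1 to +6 at 2 points depending on the mix. The mix and the gap are assumptions throughout. No shortfall from the planned power can be claimed, because that depends on reading the stated SD and means as within modality rather than for all enrolled subjects. The large losses under a running infusion are hypothetical, and stratifying would not recover them.
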